#### 2.3.1.2. Risks Associated with COVID-19 Pandemic

This clinical trial seeks to address the ongoing burden of severe Influenza infections worldwide, particularly in terms of hospitalisation and mortality, especially in clinically vulnerable groups, which remains ongoing during the covid-19 pandemic.

hVIVO implemented enhanced infection control measures during the pandemic to minimise risks of COVID-19 infection.

• Risk of increased severity of COVID-19 infection if contracted after challenge virus inoculation:

It has not been established that severity of COVID-19 infection could increase if contracted after inoculation.

Participants will be tested for respiratory pathogens, including COVID-19 on the arrival to the quarantine unit. They will be advised on protective measures and will need to follow infection control regimen.

Risk of increased severity of COVID-19 infection after SAB-176 administration

There is no evidence that severity of COVID-19 infection would increase if contracted after SAB-176 administration. Participants will be tested for COVID-19 on the day of admission to the quarantine unit. They will be instructed on the infection control measures to follow.

All participants will be instructed to follow UK Government Covid-19 guidelines and will provided with Personal Protective Equipment (PPE).

COVID-19 related emerging data will be monitored ongoingly.

### 2.3.1.3. Other Risks

#### Table 1: Risk Assessment

Potential Risk of Clinical Significance	Rationale for Risk	Mitigation Strategy									
	Study procedures										
Intravenous (IV) Catheter	The primary risks of the placement of an IV catheter include local discomfort; occasional bleeding or bruising of the skin at the site of needle puncture; haematoma; and, rarely, infection or fainting.	The participant will be closely monitored and asked about these symptoms and before being allowed to stand up.									
	Pain or bruising at the site where blood is drawn.	Blood samples will be obtained by a trained professional.									
	Syncope (fainting) can occur following or even before any blood draw as a psychogenic response to the needle insertion.	Blood samples will be obtained by a trained professional and procedures will be put in place to avoid injury from fainting.									
Blood Sampling	There is a possibility that in the process of collecting blood a nerve may be injured.	Procedure to be performed by qualified personnel.									
	Blood tests performed to address the health of the participants at screening and during the study may indicate that a participant has an infection that he/she was not previously aware of (such as human immunodeficiency virus (HIV) or hepatitis) or an unexpected illness.	The hVIVO doctor will provide the participant's general practitioner (GP), or doctor with a referral letter if the participant agrees.									
Nasal sampling	Collection of nasal wash samples or nasopharyngeal swabs may cause discomfort, sneezing, watery eyes, irritated nose, or nose bleeding.	Sample collection will be performed by appropriately qualified and trained study staff to minimise the discomfort									
	Virus infection from inoculatio	n									

Potential Risk of Clinical Significance	Rationale for Risk	Mitigation Strategy
Influenza A/California/2009 H1N1 virus infection and severe complications	Approximately 65% chance of becoming infected with Influenza A/California/2009 H1N1 virus (Sloan et al. 2020). Typical Influenza A/California/2009 H1N1 virus illness: abrupt onset of rhinitis, nasal stuffiness, fever, malaise, myalgia (muscle aches), and sore throat. Influenza, like many viruses, can cause more substantial health issues such as myocarditis (inflammation or damage to the heart muscle). However, the chance of this resulting in serious or permanent changes is rare, as most cases are minor and resolve without any lasting changes.	The safety profile of this batch of Influenza A/California/2009 H1N1 virus has been used for over 5 years by several groups globally. At hVIVO over 100 participants have been challenged with a different batch of Influenza A/California/2009 H1N1 virus. Influenza A/California/2009 H1N1 virus infection in healthy adults usually resolves without treatment within 3 to 7 days (Sloan et al. 2020). Strict inclusion and exclusion criteria will apply to ensure only healthy adults are enrolled in this study. There will be a daily medical monitoring in a Quarantine Unit for at least 8 days post-challenge. Qualified medical and nursing staff in the Quarantine Unit will monitor for and manage any symptoms. Participants will be closely followed up while being in quarantine. Electrocardiogram (ECG) will be performed, and cardiac enzymes will be tested at least 3 days, and 7 days post-viral challenge.
	Transient increase in alanine aminotransferase (ALT) or aspartate aminotransferase (AST) without clinical presentation, with a good prognosis upon improvement of infection.	ALT and AST will be monitored.
Transmission of Influenza A/California/2009 H1N1 virus to participants' close contacts	Influenza A/California/2009 H1N1 virus presence in nasal secretions can cause infection in close contacts.	Virus is usual absent from the nose by the time participants are discharged from quarantine. This will be confirmed by testing a nasal swab sample using by a qualitative virus antigen test or polymerase chain reaction (PCR) to determine

Potential Risk of Clinical Significance	Rationale for Risk	Mitigation Strategy						
		participants' suitability for departure.						
		In addition, participants will be instructed to avoid close contact with vulnerable people as described in Section 2.3.1.4 for two weeks after they leave the Quarantine Unit.						
Risk of reactivation of herpes infection.	If a participant ever had a herpes infection (e.g., cold sores, genital herpes, or shingles), there is a small possibility that this infection could return after challenge.	Participants will be instructed to inform the study staff if they currently have an active herpes infection or have had one during the 30 days before enrolment.						
Consult the Investigator's Bro	ochure for detailed information on study	y intervention.						

#### 2.3.1.4. Vulnerable Persons

For the purposes of possible contact, a vulnerable individual is a person who has close or household (i.e., share the same apartment or house) high-risk contacts including but not limited to:

- Persons ≥65 years of age.
- Children ≤2 years of age.
- Residents of nursing homes.
- Women who are pregnant or who are trying to become pregnant.
- Persons of any age with significant chronic medical conditions such as:
  - Chronic pulmonary disease (e.g., severe asthma, Chronic Obstructive Pulmonary Disease).
  - Chronic cardiovascular disease (e.g., cardiomyopathy, congestive heart failure, cardiac surgery, ischemic heart disease, known anatomic defects).
  - Contacts that required medical follow-up or hospitalisation during the past 5 years because of chronic metabolic disease (e.g., insulin dependent diabetes mellitus, renal dysfunction, haemoglobinopathies).
  - Immunosuppression or cancer.
  - Neurological and neurodevelopmental conditions (e.g., cerebral palsy, epilepsy, stroke, seizures).

#### 2.3.2. Benefit Assessment

Healthy participants in clinical studies will not receive direct benefit from treatment during their participation.

Participants may develop some immunity to Influenza A/California/2009 H1N1 virus and benefit from a general health check at Screening. Benefit may also be derived from the medical evaluations and

assessments associated with study procedures. In addition, participants are contributing to the process of developing new therapies in an area of unmet medical need.

#### 2.3.3. Overall Benefit: Risk Conclusion

Taking into account the measures taken to minimise risk to participants in this study, the potential risks identified in association with SAB-176 are justified by the anticipated benefits linked to the evaluation of SAB-176 in a viral challenge model of healthy adults, which will subsequently facilitate future assessment of influenza antibody therapies.

# 3. Objectives and Endpoints

Objectives	Endpoints	
Primary		
• To evaluate the effect of SAB-176, in reducing influenza viral load quantitative reverse transcriptase-polymerase chain reaction (qRT-PCR) when compared to placebo.	
 
VL-AUC of Influenza A/California/2009 H1N1 virus, as determined by qRT-PCR on nasal samples.
 
	
Secondary		
• To further evaluate the effect of SAB-176, in reducing viral loads / viral shedding in qRT-PCR due to Influenza A/California/2009 H1N1 virus, compared to placebo.	
 
Peak viral load as defined by the maximum viral load determined by quantifiable qRT-PCR measurements.
 
Duration of influenza quantifiable qRT-PCR measurements.
 
	

 
To evaluate the effect of SAB-176, in reducing viral loads / viral shedding in cell culture due to Influenza A/California/2009 H1N1 virus, compared to placebo.
 
	
 
Area under the viral load-time curve (VL-AUC) of Influenza A/California/2009 H1N1 virus, as determined by cell culture measurements.
 
Peak viral load as defined by the maximum viral load determined by quantifiable cell culture measurements.
 
Duration of influenza quantifiable cell culture measurements.
 
	

 
To evaluate the effect of SAB-176, in reducing symptoms due to Influenza A/California/2009 H1N1 virus, compared to placebo.
 
	
 
Area under the curve over time of total clinical symptoms score (TSS-AUC) as measured by graded symptom scoring system (categorical and visual analogue scales).
 
Peak symptom diary card score: peak total clinical symptoms (TSS) as measured by graded symptom scoring system (categorical and visual analogue scales).
 
Peak daily symptom score: Individual maximum daily sum of symptom score.
 
Number (%) of participants with Grade 2 or higher symptoms.
 
	

Objectives	Endpoints	
To evaluate the effect of SAB-176, in reducing the incidence of symptomatic infection due to Influenza A/California/2009 H1N1 virus, compared to placebo.	
 
RT-PCR-confirmed symptomatic influenza infection defined as:         
 
RT-PCR-confirmed influenza infection, AND
 
Clinical symptoms.
 
 
 
Culture lab-confirmed reduction of symptomatic influenza infection defined as:         
 
Lab-confirmed culturable influenza infection, AND
 
 
 
	
To evaluate the safety of SAB-176, when compared to placebo.	
 
Clinical symptoms.
 
Occurrence of unsolicited AEs from IV infusion up to Day 28 follow-up.
 
Occurrence of SAEs from IV infusion up to Day 28 follow-up.
 
	
To evaluate the safety of the Influenza A/California/2009 H1N1 virus challenge model.	
 
Occurrence of unsolicited AEs related to the viral challenge from viral challenge (Day 0) up to Day 28 follow up.
 
Occurrence of SAEs related to the viral challenge from viral challenge (Day 0) up to Day 28 follow up.
 
Use of concomitant medications from viral challenge (Day 0) up to Day 28 follow up.
 
	
Tertiary/Exploratory*		
To further explore the effect of SAB-176, in reducing the incidence of influenza illness due to Influenza A/California/2009 H1N1 virus, compared to placebo.	
 
Upper Respiratory Tract illness,
 
Lower Respiratory Tract illness,
 
Systemic Illness,
 
Febrile Illness,
 
Mild to moderate symptoms.
 
	
• To explore the Minimal Clinically Important Difference (MCID) in instrument change (e.g., symptom diary cards).	
 
The average amount of instrument-assessed change for all participants who rate themselves as "a little better" or "somewhat better.
 
Additional endpoints may be considered for this objective and added at a later stage.
 
	

Objectives	Endpoints
• To explore the effect of SAB-176, in reducing the incidence of infection due to Influenza A/California/2009 H1N1, virus compared to placebo.	
 
Influenza viral infection rates in upper respiratory samples by qRT-PCR and cell culture.
 

• To further explore the safety of the Influenza A/California/2009 H1N1 virus challenge model.	
 
Occurrence of haematological and biochemical laboratory abnormalities during the quarantine period.
 

• To explore the utility of wearable continuous monitoring for assessing Influenza A/California/2009 H1N1 virus infection/disease.	
 
Measures captured by continuous monitoring may be explored in relation to Influenza challenge.
 

• To explore genomic, transcriptomic, and immunological markers of Influenza A/California/2009 H1N1 virus infection, as well as the effect of SAB-176.	
 
Blood and respiratory samples may be investigated to assess i) the host baseline status, ii) response to infection, and iii) impact on SAB-176, for example:         
 
Immune markers e.g., cytokines /
 
 
 

	
 
chemokines, immunoglobulins
 
Deoxyribonucleic acid (DNA) (e.g., single nucleotide polymorphisms [SNPs],
 

	
 
genome-wide association study [GWAS])
 
Ribonucleic acid (RNA) transcriptomics (e.g., RNA sequencing, microarray)
 

	This is a non-exhaustive list.

\*Note that tertiary objectives and endpoints are optional and might be assessed only if needed; therefore, not all tests might be performed and reported.

## 4. Study Design

## 4.1. Overall Design

This is an exploratory randomised, Phase 2a, double blind, placebo-controlled study to evaluate the safety and treatment efficacy of SAB-176 against Influenza A/California/2009 H1N1 virus infection in healthy adult participants.

Up to 60 eligible participants will be randomized in a 1:1 ratio to receive either SAB-176 (up to 50 mg/kg dose) or placebo. Healthy adult participants will be pre-screened for serosuitability for Influenza A/California/2009 H1N1 virus challenge. Serosuitable participants who sign the study specific informed consent form (ICF) will be challenged with an intranasal administration of Influenza A/California/2009 H1N1 virus on Day 0. Participants will be given an IV infusion of SAB-176 or placebo on Day 1. Participants will be held in guarantine until Day 8.

The Study Schematic - showing participant progression through the study - is presented in Section 1.1; the Schedule of Activities (SoA) is presented in Section 1.2.

The total duration of study participation for a participant is approximately 5 weeks from signing study specific ICF to the participant's last scheduled visit, with the following sequence and duration of study phases:

- Screening phase: from 56 days (90 days for influenza serology) up to Day -3. Historical pre-screening data collected through the hVIVO Generic Screening process within 56 days (90 days for influenza serology) up to Day -3 may be transferred to this study after the study specific ICF has been signed by the participant.
- Inpatient phase: Participants will be resident in the Quarantine Unit for approximately 11 days (e.g., from admission on Day -2 to planned discharge on Day 8). Procedures will include:
  - Pre-human viral challenge (HVC):
    - Admission to Quarantine Unit on Day -2 / -1.
  - HVC:
    - Inoculation with Challenge virus on Day 0.
  - Post-HVC:
    - $\circ$   $\:$  IV infusion with SAB-176 or placebo on Day 1.
    - Day 1 to 7 onwards and each day study assessments will be conducted as per SoA.
    - Participants will be discharged from the Quarantine Unit on Day 8 (or may remain longer at the Principal Investigator's [PIs] discretion).

#### Outpatient phase:

• Follow-up visit: Day 28 (±3 days).

## 4.2. Scientific Rationale for Study Design

#### 4.2.1. Rationale for Study Design

The study will be conducted by hVIVO Services Limited, which has extensive experience with challenge studies. The Influenza A/California/2009 H1N1 virus strain has been shown to cause symptoms and virus shedding that closely match natural infection.

Administration of study intervention and challenge with Influenza A/California/2009 H1N1 virus will take place in hVIVO's specialised Clinical Units, either in the Quarantine Unit or Screening Clinic Units. Standard

study procedures (including collection of blood, urine, and nasopharyngeal secretions for assessment of safety and efficacy) have been employed in previous studies conducted by hVIVO.

The placebo control will be used to establish the frequency and magnitude of changes in endpoints that may occur in the absence of active treatment. Blinded treatment will enable the avoidance of bias in the interpretation of results.

Randomization will be used to minimize bias in the assignment of participants to treatment groups (active treatment or placebo), to increase the likelihood that known and unknown participant characteristics (e.g., demographic and baseline characteristics) are equally balanced across treatment groups, and to enhance the validity of statistical comparisons across treatment groups.

#### 4.2.2. Justification for Dose

A dose up to 50 mg/kg SAB-176 will be administered as a single IV infusion and is supported by the data of the previous clinical trial and the relevant non-clinical data for this investigational medicinal product (IMP). Based on the non-clinical toxicology results in New Zealand white rabbits, the no observed adverse effect level was 725.30 mg/kg/day or higher. The 725.30 mg/kg dose was the maximum dose available to test due to dose volume limitations for the species. Using body surface area calculations (FDA guidance for industry 2005) and 5X safety factor, a dose up to 50 mg/kg (the maximum therapeutic target dose for SAB-176) is equivalent to 770.8 mg/kg in rabbits.

## 4.3. End of Study Definition

A participant is considered to have completed the study if he/she has completed all phases of the study including the last scheduled visit or the last unscheduled visit as applicable. If a safety visit is required after the last scheduled visit, this will be at the PI's discretion as a duty of care, e.g., repeat spirometry or laboratory tests. These discretionary follow-up visits will not be considered part of the trial data unless they represent follow-up and closure on an AE or SAE identified during the study period.

The end of the study is defined as the date of the last scheduled visit of the last participant in the study.

## 5. Study Population

Prospective approval of protocol deviations to recruitment and enrolment criteria, also known as protocol waivers or exemptions, is not permitted.

Up to 60 participants having passed both the hVIVO Generic Screening process and meeting the inclusion / exclusion criteria of the study and inoculated with Influenza A/California/2009 H1N1 virus on Day 0, will be randomised onto the study in a 1:1 ratio active:placebo.

## 5.1. Inclusion Criteria

NO	INCLUSION CRITERIA
1	An informed consent document signed and dated by the participant and the Investigator.
2	Aged between 18 and 45 years on the day of signing the study specific ICF.
3	In good health with no history, or current evidence, of clinically significant medical conditions, and no clinically significant test abnormalities that will interfere with participant safety, as defined by medical history, physical examination, (including vital signs), ECG, and routine laboratory tests as determined by the Investigator.
4	A documented medical history prior to enrolment.
5	
 
The following criteria are applicable to female participants participating in the study.
 
a) Females of childbearing potential must have a negative pregnancy test prior to enrolment.
 
b) Females of non-childbearing potential: 
 
a. Post-menopausal females: defined as having a history of amenorrhea for >12 months with no alternative medical cause, and /or by follicle stimulating hormone (FSH) level >40mIU/mL, confirmed by laboratory.
 
b. Documented status as being surgically sterile (e.g., tubal ligation, hysterectomy, bilateral salpingectomy, and bilateral oophorectomy).
 
 
 

6	
 
The following criteria apply to female and male participants:
 
a) Female participants of childbearing potential must use one form of highly effective contraception. Hormonal methods must be in place from at least 2 weeks prior to the first study visit. The contraception use must continue until 28 days after the date of dosing with IMP. Highly effective contraception is as described below: 
 
a. Established use of hormonal methods of contraception described below (for a minimum of 2 weeks prior to the first study visit). When hormonal methods of contraception are used, male partners are required to use a condom with a spermicide:
 
 
 

Participants are eligible to be included in the study only if all the following criteria apply:

NO	INCLUSION CRITERIA
NU	
 
i. combined (oestrogen and progestogen containing) hormonal contraception associated with inhibition of ovulation: 
 
Oral.
 
Intravaginal.
 
Transdermal.
 
 
 
ii. progestogen-only hormonal contraception associated with inhibition of ovulation: 
 
Oral.
 
Injectable.
 
Implantable.
 
 
 
b. Intrauterine device.
 
Intrauterine hormone-releasing system.
 
Bilateral tubal ligation.
 
Male sterilisation (with the appropriate post vasectomy documentation of the absence of sperm in the ejaculate) where the vasectomised male is the sole partner for that woman.
 
f. True abstinence - sexual abstinence is considered a highly effective method only if defined as refraining from heterosexual intercourse during the entire period of risk associated with the study treatments. The reliability of sexual abstinence needs to be evaluated in relation
 

	
 
to the duration of the clinical trial and the preferred and usual lifestyle of the participant.
 
b) Male participants must agree to the contraceptive requirements below at entry to quarantine and continuing until 28 days after the date of dosing with IMP:
 
a. Use a condom with a spermicide to prevent pregnancy in a female partner or to prevent exposure of any partner (male and female) to the
 

	
 
IMP.
 
b. Male sterilisation with the appropriate post vasectomy documentation of the absence of sperm in the ejaculate (please note that the use of condom with spermicide will still be required to prevent partner exposure).
 
c. In addition, for female partners of childbearing potential, that partner must use another form of contraception such as one of the highly effective methods mentioned above for female participants.
 

	
 
d. True abstinence - sexual abstinence is considered a highly effective method only if defined as refraining from heterosexual intercourse during the entire period of risk associated with the study treatments. The reliability of sexual abstinence needs to be evaluated in relation to the duration of the clinical trial and the preferred and usual lifestyle of the participant.
 
c) In addition to the contraceptive requirements above, male participants must agree not to donate sperm following discharge from quarantine until 28 days
 

7	after the date of dosing with IMP. Serosuitable to the Challenge virus, as defined in the study Analytical Plan (AP).

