	
 
Admission to the Quarantine Unit on Day -2 / -1; resident in the Quarantine Unit for approximately 11 days (e.g., from admission on Day -2 to planned discharge on Day 8).
 
Inoculation with Challenge virus on Day 0.
 
IV infusion with SAB-176 or placebo on Day 1.
 
Discharge from the Quarantine Unit planned on Day 8.
 
	
	Outpatient phase: follow-up visit:	
	• Day 28 (±3 days).	
Expected duration of participant participation	Approximately 5 weeks from signing study specific ICF to the participant's last scheduled visit.	
Overall duration of clinical phase	The length of the clinical phase is estimated to last approximately 15 weeks from first participant first visit to last participant last visit.	
End of study	The end of the study is defined as the date of the last scheduled visit of the last participant in the study.	
Procedures and assessments	
 
During the study, the following assessments and procedures will be performed:
 
Informed Consent
 
Eligibility Criteria
 
Medical & Medication History
 
Demographics
 
Height & Weight and Body Mass Index
 
Alcohol Breath Testing
 
Urine Sample Collection (safety, drugs of abuse, cotinine, pregnancy)
 
Complete Physical Examination
 
Directed Physical Examination
 
Vital Signs
 
Tympanic Temperature
 
Electrocardiogram
 
Spirometry
 
Symptom Diary Cards 
 
Visual Analogue Scale
 
Patient Health Questionnaire (PHQ-9)
 
 
 
	

	
 
Generalised Anxiety Disorder Questionnaire (GAD-7)
 
Wearable, if applicable
 
Inoculation with Challenge virus
 
IV Infusion SAB-176 or placebo
 
Nasal Discharge Collection
 
Blood Sample Collection
 
Nasal Sample Collection
 
Adverse events (AEs) and Concomitant Medications.
 

Sample size	Up to 60 participants will be inoculated with the Challenge virus. Note : A participant will be considered 'enrolled' into the study once he/she has signed the study specific ICF and eligibility is confirmed and has been inoculated with the Challenge virus. Potential participants who are screened under hVIVO generic screening process for the purpose of determining suitability for the study, but do not sign the study specific ICF to participate in the study, are not considered enrolled.

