#### 8.5.3. Pregnancy Test

Female participants of childbearing potential are to have a urine pregnancy test at screening. Participants will only be enrolled if the pregnancy test is negative.

Note: Pregnancy test must be performed even if the participant is menstruating at the time of the study visit.

All female participants will have a serum sample tested for  $\beta$ -human chorionic gonadotrophin ( $\beta$ -hCG) on admission to quarantine.

Blood samples will be tested for serum FSH in post-menopausal female participants only.

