#### Sampling schedule:

Day 1 (IMP / placebo administration day): one sample pre-infusion and one sample at 1-hour post-infusion end (infusion end includes any time required for flushing), and at Days 2, 4, 6, 8, and 28.

The allowable time windows for the sampling are as follows:

- $\pm 5$  minutes from the scheduled time for time points  $\leq 1$ -hour post-infusion end.
- Allowable time windows from the scheduled time for time points >1-hour post-infusion end:
  - Day 2 timepoint (24 hours after infusion end): ±1 hour window.
  - $\circ$  Day 4 timepoint (72 hours after infusion end): ±2 hours window.
  - $\circ$  Day 6 timepoint (120 hours after infusion end): ±2 hours window.
  - $\circ$  Day 8 timepoint (168 hours after infusion end): ±2 hours window.
  - Day 28 timepoint (648 hours after infusion end): ±2 days window.
- There is no time window requirement for the pre-infusion sample. The pre-infusion PK sample must be taken on the same day prior to infusion.

Blood samples will be transported, processed, and stored in accordance with the AP. Pharmacokinetic analysis will be performed using HAI and neutralisation assays against the H1N1 strain at each participant collection timepoint. This analysis will be conducted at both hVIVO and Sponsor designated laboratories.

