## 8.18.5. Pregnancy

Details of all pregnancies in female participants and, if indicated, female partners of male participants will be collected from signing study specific ICF onwards until the last study assessment as outlined in the SoA (Section 1.2). If a pregnancy is reported, the Investigator should inform the Sponsor within 24 hours of learning of the pregnancy and should follow the procedures outlined in Appendix 3.

Abnormal pregnancy outcomes (e.g., spontaneous abortion, foetal death, stillbirth, congenital anomalies, ectopic pregnancy) are considered SAEs.

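### Pregnancy collection stops at the Day 28 (±3) visit, although the contraception window runs to Day 29 and late conceptions may not yet be detectable

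*Combined protocol and SAP*

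**What the plan says.** **Contraception window.** For female participants of childbearing potential, criterion 6a in Section 5.1 states: "The contraception use must continue until 28 days after the date of dosing with IMP". For male participants, criterion 6b sets requirements from entry to quarantine, "continuing until 28 days after the date of dosing with IMP", and adds a requirement on female partners of childbearing potential.

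**Dosing day.** The synopsis gives "IV infusion with SAB-176 or placebo on Day 1".

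**Collection of pregnancies.** Under Section 8.18.5, pregnancies in female participants and, if indicated, in partners of male participants "will be collected from signing study specific ICF onwards until the last study assessment as outlined in the SoA". Section 4.1 and the Schedule of Activities (SoA) put the last scheduled visit at Day 28, with 3 days either side.

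**Other reporting clauses.** Section 10.3.11 requires a report if a participant or partner becomes pregnant while the study is running, but ties no date to this. Section 8.18.1 covers events learned of after a participant has left the study, but only SAEs considered reasonably related. Section 10.3.1 does not count an uncomplicated pregnancy as an adverse event.

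**Tests.** The SoA schedules a urine test at screening, at the Day 28 visit and at early withdrawal. It also schedules a serum beta-hCG at admission on Day -2 or Day -1, which note i and Section 8.5.3 require in all female participants. No test is scheduled for partners.

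**The concern.** By setting a contraception window after dosing, the protocol marks out the days on which it wants no conception after exposure. One would expect a pregnancy conceived on any of those days to be reported. Section 8.18.5 instead ties collection to a visit whose nominal date falls before the window ends.

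A pregnancy also has to be recognised before it can be reported. The last scheduled test is at that same visit, so a conception shortly before it may give a negative result. For a male participant's partner, reporting depends entirely on her knowing, and on him saying so, by that date. Nothing asks participants to get in touch afterwards.

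What is at stake is complete safety reporting of pregnancies exposed to an investigational biologic, in participants who also received a live challenge virus. The primary endpoint and its analysis are not affected.

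**Working it through.** **Inputs**
- Dosing: Day 1 (synopsis; SoA).
- Contraception window: 28 days from dosing (criterion 6).
- Last visit V: Day 28 ± 3, that is Day 25 to Day 31 (Section 4.1; SoA).
- Test lag L: 10 to 14 days from conception to a positive test. **This is an assumption; the documents give no value.**

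**Checking the day count.** Section 8.16.3 gives "Day 28 timepoint (648 hours after infusion end): ±2 days window". Since 648 / 24 = 27 days, and Day 1 + 27 = Day 28, the protocol's own count is reproduced. Day 28 is 27 days after dosing, not 28.

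**Step 1: calendar gap, which needs no assumption**

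End of window = 1 + 28 = Day 29. Gap = 29 − V.

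| Last visit | Days after dosing | Gap to end of window |
|---|---|---|
| Day 25 | 24 | 4 days |
| Day 28 | 27 | 1 day |
| Day 29 | 28 | 0 |
| Day 31 | 30 | none (visit is 2 days after the window) |

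These figures are for participants who attend the follow-up visit.

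**Step 2: detection gap, which rests on the assumed lag**

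Latest detectable conception = V − L. Days of the window not observable = 29 − (V − L).

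| Last visit | Latest detectable conception (L = 14 to 10) | Days not observable (L = 10 to 14) |
|---|---|---|
| Day 25 | Day 11 to 15 | 14 to 18 |
| Day 28 | Day 14 to 18 | 11 to 15 |
| Day 31 | Day 17 to 21 | 8 to 12 |

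Across the visit window the range is 8 to 18 days. The detection gap remains at a Day 31 visit, where the calendar gap has gone.

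**Step 3: does another clause close the gap?**
- Section 8.18.1 reaches past the last visit, but only for related SAEs, and the investigator need not look for them. An uncomplicated pregnancy is not an adverse event, so it cannot enter by this route.
- Section 4.3 keeps discretionary later visits out of the trial data unless they follow up and close an AE or SAE.
- The follow-up to birth in Section 10.3.11 starts only once a pregnancy has been reported.
- The trigger in 10.3.11 has no stated end for the individual participant, and it sits awkwardly beside the explicit stop in 8.18.5.

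None of these clearly requires a pregnancy conceived inside the window but recognised after the last visit to be collected.

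**The case against.** The calendar mismatch is one day at the planned visit, and it vanishes if the visit falls on Day 29 or later. That is correct, and it is the only gap that the documents show by themselves.

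Section 10.3.11 can be read as turning on when a pregnancy arises, not when it is noticed. Section 4.3 places the end of the study at the last participant's last visit, so for many participants the study is still running after their own follow-up. This is a fair reading, but it is not what 8.18.5 says, and it would not help participants in the final quarantine group. Two sections that allow different answers need reconciling.

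Section 8.18.5 classes abnormal pregnancy outcomes as SAEs, so a related one learned of later must be notified under 8.18.1. That covers part of the ground, but not normal outcomes or outcomes that nobody reports.

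The protocol does not say that pregnancy surveillance must match the contraception window, and any fixed last visit near the end of such a window leaves late conceptions untested. With at most 60 participants and contraception required of both sexes, few events are likely. This limits the weight of the point, not its direction.

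A reader might go further and infer that pregnancies can also be missed before exposure. Criterion 5a says "Females of childbearing potential must have a negative pregnancy test prior to enrolment" without naming the test, and Section 8.5.3 places "Participants will only be enrolled if the pregnancy test is negative" straight after the screening urine test, which may date from Day -56. The documents do not support that inference. The serum beta-hCG is required in every female participant at admission and listed among the eligibility tests in Table 7. It precedes both the Day 0 eligibility review and enrolment, which occurs at inoculation. The latest scheduled test is therefore 1 to 2 days old at inoculation, not 56. What remains is a matter of wording: 5a does not point to the admission test.

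**Conclusion.** The point holds for the end of follow-up only. On the documents alone, collection closes 1 day before the contraception window at an on-time visit and 4 days before it at the earliest permitted visit; there is no calendar gap from Day 29 onwards. If a test takes 10 to 14 days to turn positive, conceptions in the last 11 to 15 days of the window would escape a Day 28 visit, or 8 to 18 days across the visit window. That second result depends wholly on the assumed lag.

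It would be tempting to express 11 to 15 of 28 days as 39% to 54% of exposed pregnancies missed. The documents do not support that. These are shares of calendar days; nothing is given on how often pregnancies would occur or how they would spread over the window.

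This is a modest gap in safety reporting, worth closing because doing so is cheap. It takes the 28-day window as given and makes no comment on its length.

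**What to change.** 1. In Section 8.18.5, state that any pregnancy in a female participant, or in the partner of a male participant, that is conceived up to the end of the contraception window in criterion 6 will be collected whenever it is recognised. Refer to the same end date in 10.3.11.
2. In the participant information, and at the last visit, ask participants to report any such pregnancy afterwards.
3. As a wording point only, let 5a and 8.5.3 cross-refer to the admission serum beta-hCG that is already required on Day -2 or Day -1.

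The cost is a few sentences in the protocol and one in the participant information. No visit or test is added. The downside is that a few reports may arrive after a participant's last visit; the consent and follow-up process for them already exists in 10.3.11.
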